4. ABBREVIATIONS

CI	Chief Investigator
CRF	Case Report Form
eCRF	Electronic Care Report Form
GCP	Good Clinical Practice
GP	General Practitioner
MIST 1	Multicentre Intrapleural Sepsis Trail 1
MIST 2	Multicentre Intrapleural Sepsis Trail 2
MIST 3	Multicentre Intrapleural Sepsis Trail 3
SSPS	Standard Study Specific Procedures
SSC	Study Steering Committee
PIS	Participant/ Patient Information Sheet
PI	Principal Investigator
NHS	National Health Service
ICF	Informed Consent Form
HRA Health Research Authority	
LDH	lactate dehydrogenase (LDH),
suPAR	Soluble Urokinase Plasminogen Activator Receptor
TP	Total protein
PAI-1	(Plasminogen-Activator Inhibitor-1
NE	Neutrophils Elastase
IL 2, 3	Interleukin 2, 3
CT chest	Computed Tomography of the Chest
CXR	Chest X Ray

ICD	Intercostal Chest Drain
VATS	Video-Assisted Thoracoscopic Surgery
IET	Intrapleural Enzyme Therapy
TUS	Thoracic Ultrasound
HRA	Health Research Authority
НСР	Healthcare Professionals
QOL:EQ-5D- 5L	Quality of life questionnaire: EuroQol- 5 Dimension
SF - 36	Short Form Survey (SF-36)
VAS	Visual Analogue Scale
ICF	Informed Consent Form
NHS	National Health Service
RES	Research Ethics Service
PI	Principal Investigator
PIS	Participant/ Patient Information sheet
R&D	NHS Trust R&D Department
REC	Research Ethics Committee
RGEA	Research Governance, Ethics and Assurance
SOP	Standard Operating Procedure

5. BACKGROUND AND RATIONALE

Pleural infection occurs when fluid gathers between the chest wall and lung and becomes infected, usually as a complication of pneumonia. Pleural infection is a frequently occurring clinical condition with 15,000 new cases in the UK annually (1). Incidence is rising in all age groups but is increasingly common in children, the immunocompromised and the elderly (2–5), who have the worst outcome (6–8). This is a serious disease and continues to be associated with high morbidity and mortality (9,10).

Impact on patients and health service:

The mean hospital length of stay (LOS) in pleural infection is 13 days (6,11) which places a significant burden on patients, their families, carers and the health service.

Unfortunately, the clinical outcomes of pleural infection have remained poor over the last two decades with a mortality rate of 20%, increasing up to 40% among elderly populations, and it is noteworthy that, 20% of patients fail initial medical treatment which includes chest tube insertion, antibiotics and intrapleural enzyme therapy and consequently these patients may require surgical operation(6,11–15). Overall, treatment of pleural infection is highly burdensome; 25% of affected individuals require hospital admission for more than a month with a median hospital stay of 12-15 days including the most recent data from the UK (6,7,11,13,15,16).

In the United Kingdom, approximately 40 patients are admitted with pleural infection daily. The cost of treating each patient in the National Health Service is approximately £4,000, equating to £58 million annually. This is largely driven by the prolonged hospital stays associated with the condition.

Implementing more efficient and evidence-based care pathways that prioritise the delivery of targeted treatments such as surgery and intrapleural therapy to patients who benefit the most is likely to enhance cost-effectiveness and reduce the length of hospital admissions.

Current practice of management of pleural infection:

Standard treatment for pleural infection involves broad-spectrum antibiotics and drainage of the pleural fluid using a tube inserted between the ribs (chest drain) and connected to a drainage bottle, which means that patients have to be admitted to the hospital for the whole course of treatment (while the chest tube in situ), and this cause discomfort and reduced mobility of the patients. Numerous studies have shown that reduced ambulation has a significant impact on recovery and rehabilitation (17). When these initial treatments fail, more aggressive treatment is required (1,18). This includes surgical treatment (Video-Assisted Thoracoscopic Surgery (VATS) or keyhole surgery) (8,19–22). However, surgery is a significant undertaking and carries significant morbidity including perioperative and anaesthetic mortality (23), a high rate of conversation to a larger operation (10-15% thoracotomy (24–26)) and up to 5% of patients suffering long term pain (27,28). An alternative to surgery is the use of enzyme therapy through the chest drain (Intrapleural Enzyme Therapy or IET) which has been proven to improve drainage and reduce hospital stay. However, IET treatment is also associated with side effects including pain and bleeding in around 4% (29).

Rationale of RAPTOR f study (feasibility clinical study):

Currently, all patients with pleural infection are treated in an identical way with initial medical treatment (drainage and antibiotics) for a period of 3 to 5 days, and then referral for further treatment (VATS or IET) if they have a poor clinical response (1). Early identification of which patients will have a poor clinical outcome would be highly valuable, as this may enable more aggressive treatment to be given early on to those that need it most, effectively personalising treatment in pleural infection.

A number of predictive factors have been identified in retrospective small-scale studies including radiological features (ultrasound)(15), pleural fluid characteristics (30) and delayed access to surgery (14). However, the only prospectively validated risk prediction model to date has been published by our unit and is called the RAPID score which reliably predicts 3-month mortality in pleural infection from 5 baseline clinical characteristics which are routinely collected in normal care.

The current national treatment guidelines for pleural infection (BTS 2023(1)) suggest the use of the RAPID score early in the treatment of pleural infection but do not specifically mandate its use, nor suggest how the score should alter treatment therefore in this study we are hoping to prove that it's feasible to assign the patient to the right treatment at the right time using RAPID score risk stratification tool.

Potential benefits of the RAPTOR f study:

Assuming the feasibility study is successful, and a definitive similar study of RAPID driven treatment is conducted – the potential of these results to directly alter patient management in pleural infection is very significant. The potential areas of benefit to patients, clinicians and the NHS are as follows:

- Targeting the right treatment to the right patients at the right time and to those that need it
 most. This includes less invasive and burdensome management (low RAPID score group) where
 this is not required as they have a better prognosis, and earlier more aggressive treatment (early
 IET or surgery for moderate to high risk group) to those at the highest risk of death. This is an
 efficient, targeted and focused resource where it is needed most, allowing fast decisions to be
 made during the illness.
- 2. Successful use of the RAPID score to alter treatment will result in fewer interventions including avoidance of unnecessary surgery and reduced time in hospital, and earlier use of the correct intervention in the illness course. This will lead to improved quality of life and less suffering, and earlier recovery with a reduction of carer burden with the potential of earlier return to work and / Or normal function.
- 3. There is the potential for a significant reduction in healthcare costs by early identification of those at the highest risk of death and prioritising invasive treatment for them, resulting in fewer interventions, shorter hospital stays and potentially shorter courses of antibiotics.
- 4. Although there is no data as yet to demonstrate this, there is a distinct possibility that using more aggressive treatment in the most unwell group will lead to reductions in the significant mortality rate of pleural infection. This would of course need to be tested in a phase 3 study after a successful feasibility study.

Patient and public involvement:

The RAPTOR feasibility study has been designed with patient and public involvement as well as embedded qualitative research methodology. On 20/10/2023, a pleural infection PPI meeting was organised via Zoom meeting at Oxford University Hospitals (OUH) NHS Foundation Trust. The 6 participants had been previously admitted to OUH for treatment of pleural infection including chest drain insertion, antibiotics plus IET or surgery, this group has been selected from 15 patients with pleural infection who have been interviewed following treatment and recovery from pleural infection, the interviews were to explore their views and experience of treatment of pleural infection and impact of their quality of life and career. The premise of the RAPTOR f feasibility study was explained to the PPI group with the aid of a draft lay summary and study flow chart. The participants supported using RAPID score to guide the management of patients with pleural infection particularly those at low risk of dying or deteriorating and this might reduce hospital stay from pleural infection. Although recognising the need for a feasibility study, the group was clear that the design should attempt to replicate a full-scale study to gain maximum information. We reviewed the recruitment process, and participants raised several points that might improve the participant experience and the recruitment rate simultaneously. Two participants joined the group in February and March 2024, and they have similar views regarding reducing the length of the hospital stay.

We discussed the practicalities of embedding qualitative research within the feasibility study to help design a future study and explore the impact of pleural infection on patients.

6. OBJECTIVES AND OUTCOME MEASURES

	Objectives	Outcome Measures
Primary	To assess the feasibility of recruitment, data collection and acceptability of the participants and of healthcare professionals of randomisation of patient with pleural infection to standard care versus RAPID care driven treatment	 30 patients randomised 1:1 between RAPID driven treatment versus standard treatment. Recruitment and retention rate, the proportion of participants screened who consented to be randomised and who consented to be interviewed. Data completeness/availability and participant completion To conduct semi-structured interviews with a proportion of the randomised participants and healthcare professionals The primary outcome will be defined as successful if ≥50% of the eligible patients are willing to be randomised and ≥ 50% of the healthcare provisional and participant agreed to take part into the interviews.
Secondary	Length of hospital stay strategies	Review completeness of data regarding the time of the participants staying in hospital over 3 months from randomisation until discharge
	Mortality rate over 3 months (all cause)	Proportion of participants who died (all cause) over 3 months post randomisation
	3. Need for IET	Proportion of participants who required IET post randomisation

4. Need for surgery	 Proportion of participants who required surgery post randomisation
5. Medical treatment failure	5. Proportion of participants who did not respond to medical treatment (pleural fluid drainage + IET) and required surgery post randomisation
6. Need for repeat intervention and admission	6. Number of participants who need further pleural procedure e.g chest drain insertion or therapeutic thoracocentesis and proportion of the participant who required re admission to hospital
7. Duration of antibiotics	7. Review completeness of data regarding the use of antibiotics from start date of antibiotics to date that has been stopped
8. Time to complete recovery and return to normal function	8. SF36 measurements
9. Health related quality of life	9. EQ5D 5I questionnaire
10. Mean change and standard deviation in breathlessness and pain	10. Serial measurement of 100mm VAS score for breathlessness and pain
11. To assess feasibility of delivering the intervention arm (RAPID driven arm)	11. Record time of failure of medical treatment to surgery (VATS, thoracotomy) or time from ICD insertion to IET

12. Healthcare	
utilisation	12. Number of pleural procedures and days in hospital post randomisation
13. To assess the pattern of computed tomography of the chest in pleural infection e.g., consolidation	13. Computed tomography of the chest to assess for consolidation
14. Radiological changes following treatment	14. Chest x- Ray to assess for pleural thickening
15. To assess if levels of pleural fluid and blood biomarkers (suPAR, PAI-1, IL 1+2, and NET) will predict treatment failure	15. The proportion of participants with an elevated level of pleural fluid and blood biomarkers in serial samples taken on day 1 (randomisation day), 3 and 5 (post - randomisation) who did not respond to medical treatment.

7. Study design

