3. SYNOPSIS

Study Title	RAPTOR – RAPID driven Treatment of Pleural Infection (feasibility study)			
Internal ref. no. / short title	RAPTOR -f			
Study registration	25/WA/0161	25/WA/0161		
Sponsor	University of Oxford Research Governance, Ethics and Assurance Team [name] [contact] [contact]			
Funder		Health and Care Research, Research on number NIHR207229	for Patient Benefit	
Study Design	Feasibility study			
Study Participants	 Adults with confirmed pleural infection requiring admission to hospital with: 1. A clinical presentation compatible with pleural infection or infective illness. 2. A pleural collection on radiology (CXR, ultrasound or CT) with a chest drain in situ or planned 3. Pleural fluid features diagnostic of infection which is either: A. purulent or B. gram positive or C. culture positive (pleural fluid or biopsy) or D. acidic with a pH<7.2 or E. low pleural fluid glucose <4.4 mmol/L or 72mg/dL(non-diabetic) or LDH ≥ 900 iu/L OR F. (non-fluid criteria) – CT findings suggestive of pleural infection (pleural enhancement) or pleural fluid septations on thoracic ultrasound 			
Sample Size	30 participants randomised (15 in each arm) from 3 to 4 centres		centres	
Planned Study Period	01/06/2025 - 01/03/2027			
Planned Recruitment period	10 months		_	
	Objectives	Outcome Measures	Timepoint(s)	
Primary	To assess the feasibility of recruitment, data collection and acceptability of the	 30 patients randomised 1:1 between RAPID driven treatment versus standard treatment. Recruitment and 	1. At recruitment completion	

			1
	participants and of Healthcare professionals of randomisation.	retention rate, the proportion of participants screened who consented to be randomised and who consented to be interviewed. Data completeness/availability and participant completion.	
		2. To conduct semistructured interviews with a proportion of the randomised participants and healthcare professionals	2. 4 to 6 weeks post hospital discharge
		3. The primary outcome will be defined as successful if ≥50% of the eligible patients are willing to be randomised and ≥ 50% of the healthcare provisional and participant agreed to take part into the interviews	3. At recruitment completion

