8. PARTICIPANT IDENTIFICATION

8.1. Study Participants

All participants with pleural infection fulfilling the inclusion are eligible for the study. Screening logs will be kept, documenting reasons for non-inclusions. The study will aim to randomise 30 patients (in a 1:1 ratio) to receive either RAPID driven treatment or standard care treatment for pleural infection.

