8.2. Inclusion Criteria

Adults with confirmed pleural infection requiring admission to hospital with ALL of the following:

- 1. A clinical presentation compatible with pleural infection or infective illness
- 2. A pleural collection on radiology (CXR, ultrasound or CT) with a chest drain in situ or planned
- 3. Pleural fluid features diagnostic of infection which is either:
 - A. purulent or
 - B. gram positive or
 - C. culture positive (pleural fluid or biopsy) or
 - D. acidic with a pH<7.2 or
 - E. low pleural fluid glucose <4.4 mmol/L or 72mg/dL(non-diabetic) or LDH ≥ 900 iu/L **OR**
 - F. (non-fluid criteria) CT findings suggestive of pleural infection (pleural enhancement) or pleural fluid septations on thoracic ultrasound
- 4. Willing and able to give written informed consent

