9.2. Screening and Eligibility Assessment

A member of the clinical team may identify participants with confirmed or suspected pleural infection. Due to the nature of the study, all participants will be in inpatient care at the time and will be offered the opportunity to participate at an early stage of their admission (by definition, within 24 hours of either confirmation of pleural infection or insertion of the chest tube for the treatment of pleural infection). The clinical team will approach potential participants and either the clinical or research team will then provide the participant with the participant information sheet and be available to answer any questions. Participants will be identified through respiratory and general wards or outpatient referrals, clinics, and ambulatory care.

There is no maximum time limit between screening and randomisation. However, due to the nature of the disease, treatment must not be delayed, so participants are likely to have less than 24 hours to consider enrolment following diagnosis of pleural infection with chest drain in situ or had therapeutic aspiration or both are planned.

Day 0 should be considered as the first contact with the research team and a decision on randomisation must be made by the end of day 1. If the participant remains eligible, randomisation is possible.

Pleural fluid samples required to confirm eligibility will be collected as part of clinical care and are not study-specific, therefore prior consent is not required. Research samples will be collected (paired blood and pleural samples) at day 1 (randomisation day), 3 and 5 post-randomisation following optional consent (agreement to collect pleural fluid 100 millilitres and blood 10 millilitres for research purposes). These samples will be transferred to the central site of the study for analysis of biomarkers.

Patients who are eligible for the RAPTOR f study but, following discussion and reading the study information sheet, decline enrolment into the study are defined as "screen failures". Despite no longer participating in the RAPTOR f feasibility study selected patients who decline entry may be invited to take part in semi-structured interviews to discuss their initial concepts and views of the study.

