The interview topic guides (for patients and for healthcare professionals) have been developed in collaboration with a pleural infection PPI group and submitted for ethical approval. The interviews will explore the following topics: acceptability of study design (e.g. recruitment, consenting, randomisation) and treatment arms; factors influencing study participation; the impact of pleural infection and study participation on the quality of life and carers; and important health outcomes.

A sample of up to 12patients who were eligible for enrolment in the RAPTOR f study will be invited to participate in interviews to ensure that that there is sufficient information for the topics covered in the interview guide and no new issues are emerging.

Healthcare Professionals Interview

Up to six healthcare professionals who will be significantly involved with the care of study participants, will be invited to participate in an interview near the end of the recruitment period. An information sheet will be provided to each of the Healthcare Professionals and a minimum of 24 hours to consider their participation. The process of obtaining consent for the interviews will mirror that used for the patient interviews, with written informed consent required prior to the commencement of the interview. This consent will include permission for the physician's comments to be recorded and for anonymised quotes to be included in the final report and any peer-reviewed literature arising from the project.

The interview topic guide will focus on the following areas:

- The experience of using the risk stratification tools, RAPID score to guide management of pleural infection.
- Suggested improvements to the study processes to optimise participant recruitment and retention.
- Understanding physician equipoise e.g. are there any patients with pleural infection that physicians would not be willing to randomise to a study of this type? What are the barriers of recruitment and randomisation
- The study's perceived effect on patient outcomes and healthcare services, as well as recommendations for future research in this field.

As with the patients' interviews, the sample size of up to six physicians has been deemed sufficient to provide enough information for the topics covered in the interview guide and that no new issues are emerging.

All interviews

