13.1. Description of the Statistical Methods

13.1.1. Analysis of the RAPTOR f feasibility study:

Feasibility parameters will be measured and reported, and include:

- Recruitment proportion (number of randomised patients divided by number of eligible patients)
- Randomisation acceptance rate (proportion of patients who are willing to be randomised over those eligible)
- Retention (number of participants who complete intended treatment, number of participants who complete intended follow up)

These will be reported and used to assess whether or not a definitive trial is feasible. Descriptive statistics will be used to describe the demographic characteristics between the two groups. For categorical variables, numbers (and proportions) will be reported for each treatment group and overall. For continuous variables, means and standard deviations (or medians in the interquartile range) will be reported for each treatment group and overall. As this feasibility study is not powered to draw definitive conclusions, comparisons between the two arms for clinical outcomes will be reported using descriptive statistics only. No statistical tests will be carried out. These will be based on multivariable linear (for continuous outcomes) or logistic (for binary outcomes) regression with adjustment for stratification factors and important prognostic factors and will be reported as adjusted differences in means (for continuous outcomes) or proportions (for binary outcomes). Treatment comparisons will be reported for the intention-to-treat population (all randomised participants will be analysed according to their allocated treatment group irrespective of which treatment they actually receive) as treatment effects together with 95% confidence intervals for the two main comparisons: (1) Standard care vs overall RAPID driven treatment (2) Low RAPID driven treatment arm vs moderate to high RAPID driven treatment arm. Compliance to the interventions will be reported.

To establish the feasibility of collecting accurate long-term outcomes in randomised participants, we will present the completeness of the outcomes across the duration of the trial. The outcome measures collected in this study will be used to inform the sample size for the future definitive large-scale phase III RCT if it is feasible to be undertaken.

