Adverse events and serious adverse events will be reported by each arm in the intervention group on the safety population only (all patients who received the allocated treatment).

It is anticipated that STATA (StataCorp LP) or other appropriate validated statistical software will be used for analysis.

13.1.2. Analysis of the embedded qualitative:

Interviews will be digitally audio-recorded, transcribed verbatim, and de-identified before being uploaded to data management software. The interview data will be analysed using Thematic Analysis. Audio-recordings will be listened to, and transcripts read and re-read for familiarisation, then opencoded to develop an initial code list. Codes will then be grouped into categories, and data explored to identify connections and to develop a descriptive account of the dataset as a whole. The analysis will

focus on the acceptability of study processes to patients, individual and group equipoise, and the patient experience of pleural infection and treatment.

For the RAPTOR-f study and embedded qualitative interviews, we will use robust progression criteria (see Table 1) to assess the feasibility of progression to a definitive phase III trial; green indicates all criteria are met, and if met, a larger study will be declared feasible. If one or more criteria are amber, this will result in mitigations including:

- o Review of qualitative data to identify barriers and potential mitigations
- o Discussion of recruitment to date and barriers with the study management group
- o Consideration of widening the recruited population and increasing centres

Table 1: Illustrate stop and go criteria for study progression, this will be applied for all centres, if any criteria are red, this will prompt major changes to the study or qualitative study design.

Criteria	Green	Amber	Red
Recruitment proportion (number eligible versus number randomised)	>50%	30% - 50%	< 30
Average monthly recruitment* (pts/centre/month)	≥1.0	0.5 – 0.9	< 0.5
Adherence to the allocated intervention group	≥90%	75% - 90%	< 75%
The proportion of key date completion (e.g Visual Analogue Score)	≥98%	75% - 97%	< 75%
Proportion completing study protocol (accounting for 10% expected attrition)	≥90%	75% - 90%	< 75%
Individual site recruitment (at 10 months)	≥10	5 – 9	< 5
Proportion completing clinicians' interview	>50 %	30% - 50%	< 30%
Proportion completing patients' interview	>50%	30% - 50%	< 30%

^{*} Once all centres have been greenlighted

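### The primary feasibility rule has conflicting denominators and cut-offs, in both its randomisation part and its interview part

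*Protocol*

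**What the plan says.** **Success rule.** Sections 3 and 6 define the primary outcome as "successful if ≥50% of the eligible patients are willing to be randomised", together with at least 50% of healthcare professionals and participants agreeing to interviews. The same cell lists a descriptive measure on another base: "the proportion of participants screened who consented to be randomised".

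**Eligibility.** Section 8.1 states: "All participants with pleural infection fulfilling the inclusion are eligible for the study". Section 8.2 requires every inclusion criterion, and the fourth is "Willing and able to give written informed consent". Exclusion 8 in Section 8.3 separately removes patients who lack capacity.

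**Decliners.** Section 9.2 describes patients who are eligible but "decline enrolment into the study are defined as" screen failures. Section 9.11 likewise counts among the eligible both those who accepted randomisation and those who did not.

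**Rates.** Section 13.1.1 defines the "Randomisation acceptance rate (proportion of patients who are willing to be randomised over those eligible", and the recruitment proportion as randomised over eligible. Section 13.2 promises separate counts of eligible, consented and randomised patients.

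**Interviews.** Section 9.11 says: "A sample of up to 12patients who were eligible for enrolment in the RAPTOR f study will be invited to participate in interviews". Up to six clinicians are invited. Section 7.2 confirms that the patient interviewees may be enrolled participants or decliners.

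**Progression table.** Section 13.1.2 includes the item "Proportion completing patients' interview" and a matching clinician item, each green above 50% and amber from 30% to 50%. The recruitment proportion has the same bands. A larger study is declared feasible when all criteria are green.

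**The concern.** The protocol uses *eligible* in two senses that cannot both hold. Under Sections 8.1 and 8.2 a patient who declines has not met inclusion 4 and is therefore not eligible. Under Sections 9.2 and 9.11 the same patient is eligible. The screen-failure label makes this worse, because a site could readily take it as a reason to leave the patient out of the eligible count.

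The interview part has a threshold but no stated base, and it does not say whether patients and clinicians are pooled. The threshold and the quantity counted also differ between Section 6 and the progression table.

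These ratios are the primary outcome and feed the decision on a definitive trial. Section 13 says that there will be no separate SAP, so no later document is planned to settle them. If the choice is left until the data are in, the result could influence the definition. Decliners logged differently across 3 to 4 centres may not be recoverable.

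**Working it through.** **Inputs.** 30 randomised (Sections 8.1 and 13.2); up to 12 patients and up to 6 clinicians invited to interview (Section 9.11); success at ≥50% (Section 6); green at >50%, amber 30% to 50%, red below 30% (Section 13.1.2).

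**The plan's own figures.** The target of 30 is 3 centres × 10 months × 1 patient per centre per month = 30 (4 centres would give 40). The definitive-trial size, taking 5% as two-sided, is 2 × (1.960 + 1.282)² × 10² / 4² ≈ 131.4, so 132 per arm and 264 in total, as stated. Neither is affected by this point.

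**1. Randomisation part: acceptance = willing / eligible.**

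- *Formal sense (8.1 and 8.2).* Every eligible patient is willing by inclusion 4. With 30 randomised, the ratio is 30/30 = 100%, apart from patients who change their minds after consenting.
- *Working sense (9.2 and 9.11).* Decliners stay in the denominator. The eligible counts below are assumed for illustration, and every willing patient is taken to be randomised.

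| Eligible, including decliners | Randomised | Acceptance |
|---|---|---|
| 40 | 30 | 75% |
| 60 | 30 | 50% |
| 80 | 30 | 37.5% |
| 100 | 30 | 30% |

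The ≥50% rule is met only if the eligible count is at most 30 / 0.50 = 60. With 100 eligible, the working sense gives 30%, the bottom of amber, and the formal sense gives 100%, green.

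**2. Interview part, patients.**

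- *Base of all 30 randomised.* The maximum is 12/30 = 40%; ≥50% needs 15 and >50% needs 16. Decliners among the 12 lower it further: with 4 of them (assumed), 8/30 = 27%.
- *Base of those screened.* At least 30 must be screened to randomise 30, so the maximum is again no more than 12/30 = 40%.
- *Base of those invited.* The maximum is 12/12 = 100%, and 6/12 = 50% meets ≥50%. If 12 is read as a cap on interviews and not on invitations, 50% stays reachable with up to 12 / 0.50 = 24 invited.

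For clinicians on the invited base, 3/6 = 50% meets ≥50%.

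**3. Cut-off and verb.** At exactly 50% the two sections disagree:

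| Result | Section 6 (≥50%) | Progression table (>50% for green) |
|---|---|---|
| 30/60 randomised | successful | amber |
| 6/12 patients interviewed | successful | amber |
| 3/6 clinicians interviewed | successful | amber |

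For interviews the numerators differ as well. Section 6 counts those who agree and the table counts those who complete, so a person who agrees and is then not interviewed counts in one and not in the other.

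**The case against.** The strongest reply is that the protocol's working use of *eligible* is clear enough. Sections 9.2 and 9.11 call decliners eligible, Section 13.1.1 defines acceptance over the eligible, Section 13.2 counts eligible and consented patients separately, and the amber and red bands for recruitment make little sense unless decliners are in the denominator. A consent item among the inclusion criteria is routine. The sentence that introduces the screen-failure label itself calls those patients eligible.

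Most of this stands, and it limits the point. A reader might infer that acceptance is 100% by definition and that the rule cannot be evaluated. The documents do not support that: in the working sense the rate can be computed and is informative. A reader might also infer that the interview part can never be met because 12 of 30 is 40%. That ceiling needs all randomised patients as the base. Section 6 suggests this base by describing the interviews as held with part of the randomised group. Section 9.11 suggests those invited, and because decliners may be among the 12, they need not be a subset of the 30.

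The screened measure is descriptive and does not by itself compete with the success rule. The gap between ≥50% and >50% matters only at exactly 50%, and amber leads to mitigation, not failure. Agreement and completion may both be worth reporting. Even so, exactly 50% is a possible result with bases of 12 and 6, and nothing in the protocol says which reading governs.

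**Conclusion.** The point holds as an internal inconsistency in the primary success rule. Its size depends on the reading:

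- Acceptance is close to 100% if the formal definition or the screen-failure label is used to drop decliners. If decliners are kept, it is an informative rate that passes only with 60 or fewer eligible patients.
- The patient-interview criterion is out of reach at 40% on a base of 30 randomised, and reachable on a base of those invited.
- A result of exactly 50% is a success in Section 6 and amber in Section 13.1.2.

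This assumes that 30 are randomised and that the caps of 12 and 6 hold; the eligible counts other than the limit of 60 are illustrative. The rule can be evaluated once a reading is chosen, but the protocol does not choose one. Because the ratios decide progression, the choice should be fixed before screening data accumulate.

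**What to change.** 1. Define one denominator for acceptance and recruitment proportion: patients who meet inclusion 1 to 3 and have no exclusion criterion, leaving out the willingness part of inclusion 4. Keep exclusion 8 in force, so that patients who lack capacity are not counted as unwilling, and report them separately in the participant flow.
2. Log those who decline as eligible, declined, and stop calling them screen failures.
3. State the interview base as those invited, separately for patients and clinicians.
4. Use one verb and one cut-off in Sections 3, 6 and 13. If both agreement and completion are of interest, report both but tie the threshold to one.

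The cost is a wording amendment and one screening-log field. Reported acceptance may be lower than under the formal definition; for a site already counting decliners as eligible, it should not change on that account.
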